1.2 Study Design

.See Protocol of the study

1.3 Treatment Groups

Treatment groups: NR-RTX and R-GC or NR-GC.

1.4 Power Calculation

No power calculation was performed due to the lack of data from any similar study of RTX in GC non-responders

2 STUDY VARIABLES

2.1 Baseline Variables

2.1.1 Demographics and Baseline Characteristics only available at baseline

- Age (years)
- Sex (man /woman = m/w)
- Smoking status (smoker/previous smoker/non-smoker)
- Previous treatment (operation/RAI/ATD)
- Current treatment (Levothyrocin/ATD)
- Time from diagnosis of GD (years)
- Duration of eye symptoms (months)

2.1.2 Laboratory/evaluation measurements only available at baseline:

- fT4 (pmol/L)
- fT3 (pmol/L)
- TSH (mIE/L)
- Exophthalmometry left (mm)
- Exophthalmometry right (mm)
- Subjective diplopia (non/intermittent/corrected with prism)

2.2 Variables evaluated throughout the study

- TRAb antibodies
- Waist circumference change (%)

- High systolic blood pressure (ja/nej)
- High diastolic blood pressure (ja/nej)
- ALT increased (ja/nej)
- AST increased (ja/nej)
- OGTT results (diabetes/glucose intolerance)
- Short ACTH test (normal/inadequate response)
- Collected information on patient-reported adverse events

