Does RTX lower the CAS of the non-steroid responsive TAO-patients (NR-RTX), in comparison to NR-C, that continued with iv GC, and R-GC? Do the background variables differ between NR-RTX and NR-GC or R-GC? And lastly, does the QoL differ between the R-GC and the NR-RTX at given measuring points?

Material and Methods

Study design

The RTX-study is a non-randomized prospective study that covers patients with moderate-severe TAO with indication for treatment with iv GC. For this study, a control group (NR-C) will be created.

Patients with TAO are evaluated at Department of Ophthalmology at Sahlgrenska University Hospital/ Mölndal's and are asked for participation if eligible. Variables collected at each visit Clinical Activity Score (CAS), Quality of Life (QoL) through ThyPRO self-assessment questionnaire, biochemical tests (fT4, fT3, TSH, TRAb, liver function tests, fasting blood glucose), blood pressure and waist. An oral glucose tolerance test (OGTT) is performed at 12, 18, and 46 weeks, and a short adrenocorticotrophic hormone (ACTH) test at 12 and 46 weeks. Dual-energy x-ray absorptiometry (DXA) of the spine is conducted at 0 and 18 weeks.

All patients in the RTX-study start the 12-week scheme of iv GC at baseline. After four weeks of treatment, an evaluation of the treatment outcome is made. If the patients have improved their CAS score by ≥ 2 points, they are classified as responders to iv GC (R-GC) and continue their 12-week iv GC scheme. The remainder of the patients are classified as non-responders to the treatment with iv GC and are switched to 1000 mg iv RTX in week 5 and 7, combined with a weekly oral dose of 12.5 – 15 mg MTX (NR-RTX). The RTX is administered at the department of Rheumatology at Sahlgrenska University Hospital. All included patients have thereafter follow-up visits at week 12, 18, 32, 46 and 68 weeks after baseline.

At week 18 and at all follow-up timepoints thereafter, patients in R-GC group are evaluated for possible relapse. If a patient in R-GC has a CAS ≥ 4 points and CAS has worsened by ≥ 2 points compared to the value measured in the prior evaluation time-point, the patient is

considered having a relapse. Patients with relapse are randomized to either treatment with RTX and MTX or with *per oral* GC and MTX.

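### Blood pressure, ALT and AST enter the SAP only as yes/no flags with no stated cut-off or baseline reference, and fasting glucose is unused, so abnormality present before treatment can count as a group difference

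*SAP*

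**What the plan says.** SAP 2.2 gives four safety variables in yes/no form (ja/nej is Swedish for yes/no): "High systolic blood pressure (ja/nej", "High diastolic blood pressure (ja/nej", "ALT increased (ja/nej" and "AST increased (ja/nej". No cut-off, baseline rule or shift rule accompanies any of them. The same list has "Waist circumference change" as a percentage, so for waist the SAP does plan a change. Glucose metabolism appears only as "OGTT results (diabetes/glucose intolerance". Fasting glucose is in no SAP list.

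The protocol, under Study design, has these quantities measured at each visit: "liver function tests, fasting blood glucose), blood pressure and waist". It also states: "An oral glucose tolerance test (OGTT) is performed at 12, 18, and 46 weeks". No OGTT is scheduled at baseline.

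SAP section 3 assigns tests by variable type: Mann-Whitney for continuous variables between groups, Fisher's exact test for dichotomous ones, and Wilcoxon's signed-rank test within groups for continuous variables only. SAP 1.4 reports that no power calculation was made.

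**The concern.** A flag recorded at a visit describes status at that visit. A patient who was hypertensive before the first infusion is a yes at follow-up whatever the treatment did. In a randomised trial such patients would be balanced on average. Here the protocol calls the study non-randomised, and NR-RTX and R-GC are formed by response to four weeks of iv GC, so their baseline shares of hypertension or raised liver enzymes may differ. Fisher's test on the flag would read that difference as a group difference in safety.

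Two further losses follow. Cutting a measured value at a threshold discards information, which matters in what is likely to be a small NR-RTX group. And because the only within-group test is for continuous variables, the flags have no planned within-patient comparison.

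Glucose has a related gap. Without a baseline OGTT, intolerance first seen at week 12 cannot be separated on OGTT from intolerance that was already there. Fasting glucose is the only scheduled glucose measure that reaches back to baseline, and the SAP does not use it.

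**Working it through.** The plan states no sample size, power or effect for these variables, so there is no figure of its own to reproduce. Everything numerical below rests on assumptions, shown as ranges.

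**Inputs from the documents.** Form of each variable (SAP 2.2); tests by variable type (SAP section 3); measurement at each visit and OGTT timing (protocol, Study design).

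**Assumed inputs.** Two-sided 0.05; normal data; groups of 10:40 and 15:35 (50 patients with 20% or 30% in NR-RTX); true difference 0.3, 0.5 or 0.8 SD; baseline/follow-up correlation r of 0.3-0.7; 10-50% abnormal.

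**1. How much of the follow-up yes count was already there?** Assume no treatment effect and a share q abnormal at both times. The share already yes at baseline is P(abnormal at both times) / q, from a bivariate normal with correlation r.

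| q | r = 0.5 | r = 0.7 |
|---|---|---|
| 10% | 0.0324/0.10 = 32% | 0.0468/0.10 = 47% |
| 20% | 0.0872/0.20 = 44% | 0.1129/0.20 = 56% |
| 30% | 0.1568/0.30 = 52% | 0.1905/0.30 = 64% |

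**2. What could baseline imbalance do?** As an illustration, let the baseline shares be 40% in NR-RTX and 15% in R-GC, with treatment changing nothing. Fisher's test on follow-up status is then significant in about 39% of trials at 10:40 and 45% at 15:35.

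**3. How much information does the cut keep?** Asymptotic efficiency relative to the measured value is φ(z)² / [q(1 − q)], where z is the cut that leaves a share q above it.

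- q = 50%: 0.3989²/0.25 = 0.64
- q = 30%: 0.3477²/0.21 = 0.58
- q = 20%: 0.2800²/0.16 = 0.49
- q = 10%: 0.1755²/0.09 = 0.34

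**4. Power on the follow-up value against the flag.** Mann-Whitney was simulated and Fisher enumerated exactly. At 0.8 SD:

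| Groups | Mann-Whitney | Fisher, cut at median | Fisher, cut at 75th percentile |
|---|---|---|---|
| 10:40 | 0.57 | 0.30 | 0.39 |
| 15:35 | 0.70 | 0.38 | 0.49 |

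With the 90th percentile added as a cut, the advantage of the measured value is about 2-9 points at 0.3 SD, 7-18 at 0.5 SD and 16-32 at 0.8 SD.

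**5. Power on change from baseline.** This is the comparison that bears on the fix. The SD of change, in units of the SD of one value, is √[2(1 − r)]: 1.18 at r = 0.3, 1.00 at r = 0.5 and 0.77 at r = 0.7. Change is therefore noisier than the follow-up value below r = 0.5 and less noisy above it. At 10:40 and 0.8 SD, Mann-Whitney on change has power 0.42, 0.57 and 0.78 at these three correlations. Against the flag at the median (0.30) that is a gain of 12, 27 and 48 points. Against the 75th percentile (0.39) it is 3, 18 and 39. Over both splits, 0.3-0.8 SD and r of 0.3-0.7, the gain is about 0-52 points.

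**The case against.** The strongest reply is that these variables are outside the declared analysis set. SAP 2.3 lists CAS, adverse-event frequency and TRAb; blood pressure, ALT, AST and OGTT stand only in 2.2. Threshold reporting of safety values is conventional, and baseline flags may be available to show imbalance. This stands as a limit on importance. It does not remove the point: section 3 assigns tests by variable type without restriction to 2.3, and no rule says the baseline flags will be used.

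Several stronger readings are tempting, and the documents do not support them.

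- A reader might infer a fixed power loss, such as 20-30 points. With no group sizes, effects or abnormality rates stated, no single figure belongs to this trial. A wider grid, from 10:10 to 50:50 patients and 0.3 to 1.2 SD, gives about 0 to 43 points for the follow-up value against the flag.
- A reader might take the 70-80% steroid response in the protocol's Background as giving the group split. That figure concerns early treatment and carries no response definition, whereas NR-RTX is defined by a CAS improvement of less than 2 points at four weeks. The 10:40 and 15:35 splits are assumptions.
- A reader might say glucose is also reduced to yes/no. OGTT is listed with two named abnormal categories.
- A reader might say the ALT and AST flags certainly ignore baseline. The word used could mean a rise from baseline; it is undefined. Prior abnormality can count as a finding, but it is not certain to.
- A reader might treat fasting glucose as a full replacement for a baseline OGTT. Nothing in the documents shows that it identifies prior intolerance on OGTT.

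**Conclusion.** The concern holds as a minor analysis point. Blood pressure, ALT and AST are planned only as flags without a stated cut-off or baseline reference, and fasting glucose is not used, although the measured values are collected at each visit.

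The main consequence is interpretation: in non-randomised groups, prior abnormality can be read as a group difference. Under the assumptions in step 1, roughly a third to two thirds of follow-up yes results would predate treatment. The loss of power is real in direction, but its size depends on unstated quantities. The gain from analysing change is close to nothing when the effect is small and the correlation low, and large when both are high.

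The missing baseline OGTT is a limit of the design that SAP wording can only partly offset. The primary CAS analysis is unaffected.

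**What to change.** In SAP 2.2:

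1. Add change from baseline in systolic pressure, diastolic pressure, ALT, AST and fasting glucose as continuous variables. Test them by the Mann-Whitney rule between groups and the Wilcoxon rule within groups, both already in section 3.
2. Keep the flags, state the cut-off for each, and say whether increased ALT or AST means above a limit or above baseline. Alongside overall status, report new abnormality among patients normal at baseline.
3. Show OGTT results for all patients and also by baseline fasting glucose, with a sentence saying that this only partly substitutes for a baseline OGTT.

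No new data or new test is needed. The costs are a few more table rows, some extra safety tests to be labelled descriptive, and a smaller denominator for the new-abnormality counts. With 10-30% abnormal at baseline, for example, a group of 10 falls to 7-9 (10 × 0.7 to 10 × 0.9). That is why those counts should sit beside the measured changes and not replace them.

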2.3 Analysis Variables

2.3.1 Primary Variable

- Change of CAS (clinical activity score) between the observation timepoints and the previous timepoint: comparison between the treatment groups
- CAS: comparison between the treatment groups at the different timepoints

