PROTOCOL

TITLE. Rituximab (RTX) Therapy in Patients With Active TAO

NCT 02378298

Date 2011-08-24

Background

Every year, 2000 patients in Sweden get the diagnosis of a diffuse autoimmune hyperthyroidism (Grave's disease (GD)). About 40% of the patients with GD have some complaints from their eyes indicating thyroid associated ophthalmopathy (TAO) in its mild form. Moderate-severe forms are seen in approximately 5-10% of GD patients. TAO is an autoimmune complication of GD and the inflammation causes swelling of the periorbital fat, muscles and connective tissue. The patient obtains symptoms such as red eyes, pain, epiphora, diplopia and sometimes exophthalmos. This affects the patient's quality of life (QoL) negatively.

Today, the primary treatment of moderate-severe TAO is high doses of intravenous (iv) steroids, with the purpose to suppress the inflammation. High doses of iv steroids cause side effects, therefore, it is motivated only in moderate-severe cases. Even when the treatment is given early in the course of the disease, only 70-80% of the patients respond to the treatment (responders). The treatment effect on the inflammation is most commonly measured with Clinical Activity Score (CAS) – a score recommended by the European Group of Graves orbitopathy (EUGOGO).

Ten years ago, small observational studies reported promising result on Rituximab (RTX) treatment in TAO, given less side-effects. RTX is an immunomodulating drug where antibodies affect B-cells.

Objectives

The primary aim of this study is to evaluate the effect of Rituximab (RTX) in Thyroid Associated Ophthalmopathy (TAO) patients who are non-responsive to treatment with iv GC (NR-RTX), with patients controls that continued with iv GC even though they did not respond (NR-C). A second aim is to compare the NR-RTX patients with the steroid responsive ones (R-GC) and NR-C, regarding background variables (gender, age, smoking status, duration of GD, duration of eye symptoms, thyroid treatment and lab) and efficacy variables (CAS, CAS SU/M, severity, proptosis and subjective diplopia). Lastly, a third aim is to evaluate and compare the QoL between the R-GC and the NR-RTX in the study at given time points.

Research questions

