All patients included in the study are assessed according to study protocol, but if DON is developed, the affected patient is treated outside the study protocol in order to follow DON treatment regimen. The patients with DON still have the same evaluation time points as the other patients in the study, but they are excluded from the comparisons between groups after the occurrence of DON.

From the group of patients with moderate – severe TAO with indication for treatment with iv GC that do not meet inclusion/exclusion criteria for the RTX-study or declined participation, a control group (NR-C) of non-responders will be created. As they are not included in the RTX study, they continue with their 12 weeks scheme of iv GC treatment.

Data collected at the follow-up timepoints: QoL, safety data and information on adverse events.

Study population

Inclusion criteria for the RTX study: man or woman between 18-70 years old, TAO with 7-point score system of CAS ≥ 4 (less than 3 months old), euthyroid for at least 6 weeks.

Exclusion criteria for the RTX study were: DON, ulcerative corneal involvement, previous treatment with steroids for TAO (except for prophylaxis for TAO in connection with RAI), previous treatment with RTX, positive Hepatitis B or C serology, obtained a living vaccine within 4 weeks prior RTX+MTX to evaluation, history of recurrent significant infection or history of recurrent bacterial infections, assessment by the investigator that the patient may not attend to the protocol, current pregnancy or lactation, significant cardiac disease, including significant or uncontrolled arrhythmia, previous active tuberculosis, bone marrow depression with leukopenia, thrombocytopenia or significant anaemia, allergy to the active substance or any other substance in the medications or murine proteins, active, severe infections (such as tuberculosis, sepsis or opportunistic infections), patients with severe immunosuppression, severe cardiac failure or severe uncontrolled heart disease.

The TAO patients not included in the RTX-study will be identified using the diagnosis-related group (DRG) registry according to the 10th revision (ICD-10) in VGR. In DRG, a combination of different codes was used (TAO [H06.2], Graves' disease [E05.0] and iv infusion [DT016]).

Efficacy variables

In the study, both patients' eyes are evaluated regarding CAS and the score of and any improvement of the worst eye was used.

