1 STUDY DETAILS

1.1 Study Objectives

- A. Do the background variables differ between NR-RTX and R-GC or NR-GC?
- B. Does RTX lower the CAS of the non-steroid responsive TAO-patients (NR-RTX), in comparison to NR-C, that continued with iv GC, and R-GC?

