3 STATISTICAL METHODOLOGY

Tests between groups will be made for the NR-RTX group and all of the other groups one at a time; R-GC and NR-C (where applicable).

For continuous variables Mann-Whitney U-test will be used for analyses between two groups. For dichotomous variables Fisher exact test will be used for test between two groups. For ordered categorical variables Mantel Haenszel Chi Square test will be used for test between two groups.

For all continuous variables Wilcoxon's Signed-Rank test will be used for within group analyses.

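### SAP 2.3.1 makes two CAS variables primary at every visit, with no primary visit, significance level or multiplicity rule: up to 10 post-switch primary tests against NR-C

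*SAP*

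**What the plan says.** SAP 2.3.1 is headed in the singular but has two entries: "Change of CAS (clinical activity score) between the observation timepoints and the previous timepoint: comparison between the treatment groups" and "CAS: comparison between the treatment groups at the different timepoints". No visit is singled out in either.

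SAP section 3 compares NR-RTX with "all of the other groups one at a time; R-GC and NR-C (where applicable"). It assigns tests by type of variable, for example "For continuous variables Mann-Whitney U-test will be used for analyses between two groups", and a Mantel-Haenszel chi-square test for ordered categorical variables. It does not say which type CAS is. It states no significance level, sidedness, testing order or adjustment. SAP 1.4 reports that no power calculation was done, so no primary test can be inferred from one.

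The protocol's Objectives make the primary aim a comparison of NR-RTX "with patients controls that continued with iv GC even though they did not respond (NR-C"). R-GC belongs to the second aim. SAP 1.1, objective B, asks about CAS "in comparison to NR-C, that continued with iv GC, and R-GC", so it sets the two comparators side by side.

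Under Study design, RTX is given in weeks 5 and 7, and included patients are then seen at weeks 12, 18, 32, 46 and 68. NR-C patients come from those "that do not meet inclusion/exclusion criteria for the RTX-study or declined participation". They are outside the RTX study, and no CAS schedule is given for them.

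Change of CAS from baseline is planned, but SAP 2.3.2 makes it secondary.

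**The concern.** A primary analysis should yield one answer to the primary aim, or several answers with a rule for combining them. Here any of up to ten p-values against NR-C could be called the primary result, and no rule limits the chance of a false positive across them.

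The two variables also measure different things. CAS level shows where the groups stand at a visit. Change since the previous visit shows only what happened in that interval. After week 12 that interval no longer contains the switch: a benefit that is held scores zero, and a benefit that fades counts in favour of control. The SAP does not say which variable decides when they disagree.

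**Working it through.** **No figure to reproduce.** The documents give no significance level, sample size or error rate. Those used below are assumptions.

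**Count of tests.**
- Primary variables: 2 (SAP 2.3.1).
- Visits after the switch: 5 (weeks 12, 18, 32, 46, 68; protocol, Study design). Week 4 precedes the switch and is not counted.
- Comparator: NR-C only (protocol, Objectives).
- Ceiling: 2 x 5 = 10. With NR-C data at weeks 12 and 18 only: 2 x 2 = 4. At week 12 only: 2 x 1 = 2.

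**Upper reference, independent tests at 0.05: 1 - 0.95^k.**
- k = 10: 0.401. k = 4: 0.185. k = 2: 0.0975.

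The tests are not independent, since the same patients recur and each change is a difference of two levels. So 40% overstates the rate.

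**Simulated error with no true difference.** Assumed: CAS rounded to 0-7, SD 1.4, 15 or 30 per group, between-visit correlation 0.3-0.7 (constant, or declining with distance between visits), tie-corrected Mann-Whitney at two-sided 0.05.

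| NR-C visits with CAS | Tests | Chance of at least one p<0.05 |
|---|---|---|
| All five | 10 | 29-35% |
| Weeks 12 and 18 | 4 | 14-17% |
| Week 12 only | 2 | 8-10% |
| One named test | 1 | about 5% |

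Moving the mean CAS between 2 and 5 changes the ten-test figure little (30-36%).

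**What each variable sees.** Let d(t) be the NR-RTX minus NR-C difference in mean CAS at week t. The level test targets d(t). The visit-to-visit test targets d(t) - d(previous t).

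Take d(4) = 0 and a benefit held from week 12, d(12) = d(18) = -1.5:
- Step 4-12: -1.5 - 0 = -1.5. Power is about 62-91% at 15 per group and 89-100% at 30. This needs a week-4 CAS for NR-C.
- Step 12-18: -1.5 - (-1.5) = 0. Significant in about 4-6%, which is chance.
- Level at week 18: -1.5. Power is about 77% at 15 per group and 97-98% at 30.

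If the benefit then shrinks to -b, with 0 < b < 1.5, the next step is -b - (-1.5) = 1.5 - b > 0. That favours control although CAS is still lower on RTX.

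**Trade-off in choosing the single variable.** With a constant 0.5-point group difference present before the switch and no RTX effect, unadjusted week-18 level gives p<0.05 in about 14-27% of trials (15-30 per group). Change from week 4 to week 18 gives about 5%. For the 1.5-point benefit at 15 per group, change from week 4 has about 51-91% power, against about 77% for level.

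**The case against.** **This is a small non-randomised study, and all comparisons are planned.** A reader might infer that the investigators mean to pick the best p-value after seeing the data. The documents do not support that: the SAP plans every comparison and proposes no selection. What stands is that nothing in it prevents selection. The SAP labels these variables primary and does not call them exploratory, and lack of a power calculation does not prevent naming one test.

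**NR-C may have few visits.** This is fair, and it is why ten is only a ceiling. Section 3 itself qualifies the comparison as made where applicable. With week 12 alone, two tests remain and the inflation is modest. A week-4 CAS for NR-C is likely, because the only rule for non-response is the week-4 CAS change, but the documents do not confirm it.

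**Visit-to-visit change is not useless.** A reader might infer that this variable cannot detect a held benefit. That is too strong: its 4-12 step spans the switch and has reasonable power. The criticism applies only to the later steps. The planned change from baseline would also show a held benefit, but it is secondary.

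**Both comparators might be counted.** Objective B and section 3 could be read as giving 20 primary tests. The protocol places R-GC in its second aim. R-GC is also selected on a CAS fall of at least 2 points by week 4, so a false-positive rate under equal groups is not the right description of that contrast. It is not counted here.

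**Confounding matters more.** It may, but it is a separate problem and does not excuse an undefined primary test.

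**Conclusion.** The point holds and should be fixed. Followed as written, the plan allows up to ten post-switch primary tests against NR-C, with no rule saying which one answers the primary aim. That follows from the text alone. The size depends on assumptions: 0.05 per test, 15-30 per group, SD 1.4, correlation 0.3-0.7 and Mann-Whitney. On those, the chance of at least one nominally significant primary result with no true difference is about 29-35% at the ceiling, falling to 8-10% if NR-C has only week 12. These rates describe multiplicity alone, not bias from how NR-C is formed.

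The disagreement between the two variables is real but limited to steps after week 12.

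One part of the SAP, ahead of section 1, was not in the text available. The conclusion rests on the sections that were.

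**What to change.** 1. State the weeks at which CAS is recorded for NR-C, including whether week 4 is among them.
2. Name one primary test: NR-RTX against NR-C, on one CAS variable, at one post-switch visit at which NR-C has CAS (for example week 18, otherwise week 12), two-sided at 0.05.
3. Say whether CAS is treated as continuous or ordered categorical, and name the test accordingly.
4. Decide in advance whether the variable is CAS level, or a change from (or adjustment for) a pre-switch CAS, and justify it. It should not be change from the previous visit after week 12.
5. Make the other visits against NR-C secondary, in a fixed order or with Holm's adjustment. Make later visit-to-visit changes descriptive. Keep R-GC comparisons outside the primary test, in line with the protocol's second aim.

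The cost is SAP wording and a check of the NR-C records; no treatment or visit changes. Only one result can then be called primary. The choice in step 4 trades power against sensitivity to pre-switch differences, and neither option is better throughout. Naming one test does not remove confounding from NR-C being ineligible or declining patients, so the report should say so beside the primary result.

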2.3.2 Secondary Variables

- Change of CAS between the observation timepoints and the baseline: comparison between the treatment groups
- Comparison of frequency of adverse events between NR-RTX and R-GC.
- TRAb antibodies

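### One of the two primary variables, CAS change from the previous visit, captures the rituximab response only at week 12; afterwards a held response scores zero and can contradict the other primary variable, CAS level

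*SAP*

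**What the plan says.** SAP 2.3.1 lists two primary variables without ranking them. One is "Change of CAS (clinical activity score) between the observation timepoints and the previous timepoint", compared between treatment groups. The other is "CAS: comparison between the treatment groups at the different timepoints". SAP 2.3.2 adds, as secondary, "Change of CAS between the observation timepoints and the baseline: comparison between the treatment groups". Since change from baseline is listed separately, the previous timepoint must mean the preceding visit. The protocol's relapse rule also compares CAS with the preceding evaluation. The SAP names no deciding visit and does not say which primary variable decides.

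The protocol (Material and Methods, Study design) fixes the timing:

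- Week 4: "After four weeks of treatment, an evaluation of the treatment outcome is made".
- Study patients who have not responded by then are "switched to 1000 mg iv RTX in week 5 and 7".
- Follow-up: "All included patients have thereafter follow-up visits at week 12, 18, 32, 46 and 68 weeks after baseline".
- Controls: "As they are not included in the RTX study, they continue with their 12 weeks scheme of iv GC treatment".

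SAP 3 tests continuous variables between groups with the Mann-Whitney U-test and within groups with Wilcoxon's signed-rank test. SAP 1.4 reports that no power calculation was done.

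**The concern.** The primary aim is the effect of RTX in NR-RTX compared with NR-C, and the research question is whether RTX lowers CAS. A short course that works should lower CAS from its pre-RTX value and keep it lower. A variable whose reference moves forward at every visit measures something else after week 12, namely how much CAS changed in the latest interval. The group that responded early and stayed well has nothing left to gain, while a group improving slowly keeps recording falls. Both primary variables are tested at the same visits with no rule between them. The plan could therefore produce two primary results that point in opposite directions on the same data, and either could be reported.

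**Working it through.** **Step 1: which interval each change covers (documents only).** With RTX in weeks 5 and 7, change from the previous visit runs over these intervals:

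| Visit (week) | Reference (week) | Reference before RTX? | Score if response is held from week 12 |
|---|---|---|---|
| 12 | 4 | yes | full response |
| 18 | 12 | no | 0 |
| 32 | 18 | no | 0 |
| 46 | 32 | no | 0 |
| 68 | 46 | no | 0 |

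The zeros are arithmetic and need no assumed figure.

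**Step 2: direction against a slowly improving control (assumed means).** The documents give no CAS paths, SDs or group sizes, so there is no plan figure to reproduce. Assume mean CAS at weeks 4/12/18/32/46/68 of 5/2.5/2.5/2.5/2.5/2.5 in NR-RTX and 5/4.5/4.0/3.6/3.3/3.0 in NR-C. The difference in visit-to-visit change is (RTX now − RTX previous) − (NR-C now − NR-C previous). The difference in level is RTX now − NR-C now.

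| Week | Visit-to-visit change | Level (here also change from week 4) |
|---|---|---|
| 12 | −2.5 − (−0.5) = −2.0 | 2.5 − 4.5 = −2.0 |
| 18 | 0 − (−0.5) = +0.5 | 2.5 − 4.0 = −1.5 |
| 32 | 0 − (−0.4) = +0.4 | 2.5 − 3.6 = −1.1 |
| 46 | 0 − (−0.3) = +0.3 | 2.5 − 3.3 = −0.8 |
| 68 | 0 − (−0.3) = +0.3 | 2.5 − 3.0 = −0.5 |

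The right column is the running sum of the middle one (−2.0 + 0.5 = −1.5, and so on). The positive entries show only that the RTX lead is shrinking. Tested alone, they read as benefit for NR-C.

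**Step 3: how often a test would say so.** Further assumptions: between-patient SD 1.0, visit SD 0.8, integer CAS limited to 0–7, 20 per group, mean CAS flat at 5 over weeks 0–4, Mann-Whitney at two-sided 0.05. Repeat runs differ by one or two percentage points.

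| Variable | Favours | Wk 18 | Wk 32 | Wk 46 | Wk 68 |
|---|---|---|---|---|---|
| Change from previous visit (primary) | NR-C | 24% | 17% | 12% | 11% |
| Change from previous visit (primary) | RTX | at most 0.3% | at most 0.3% | at most 0.3% | at most 0.3% |
| CAS level (primary) | RTX | 94% | 75% | 45% | 21% |
| Change from baseline (secondary) | RTX | 96% | 78% | 50% | 23% |
| Change from week 4 (not planned) | RTX | 97% | 78% | 52% | 23% |

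At week 12 the visit-to-visit variable favoured RTX in 100% of runs. With 12 per group it favoured NR-C in 9–16% at weeks 18–68.

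**Step 4: sensitivity.**

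- Other paths: NR-RTX 5/2/2/2/2/2, NR-C 5/4.6/4.2/3.8/3.4/3.0, both SDs 0.7. Visit-to-visit change at weeks 18–68 favoured NR-C in about 11% of runs (10 per group) or 20% (20 per group), and RTX in 0.4% or less.
- NR-C flat after week 12, Step 2 setting: visit-to-visit change favoured either group in only 2–3% of runs, the nominal rate. The reversal disappears, but so does any sign of the held RTX benefit.

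**The case against.** The strongest reply is that the SAP already holds what is needed. CAS level has the same primary rank, shows a held difference at every visit, and in the illustration performs nearly as well as change from a fixed reference. Change from baseline is already planned as secondary. A reader might infer from the flaw that follow-up to week 68 cannot answer whether RTX lowers CAS. The documents do not support that, because the other primary variable can show it.

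A reader might also infer that the result will turn in favour of NR-C. That does not follow either. It requires NR-C to keep improving after week 12, on which the documents are silent. It also requires NR-C to be measured at those visits. The follow-up schedule is written for included patients, NR-C are outside the RTX study, and SAP 3 tests groups only where applicable.

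A third inference is that week 4 should become the reference everywhere. Week-4 CAS helps decide who is a non-responder, so patients scoring high by chance at week 4 are over-represented and would tend to fall later without any effect of RTX. Within NR-RTX that regression to the mean would favour RTX. Between the two non-responder groups it acts on both, though perhaps not equally. Nor is change from baseline disqualified by the four weeks of iv GC it includes: both non-responder groups received iv GC, so that part should largely cancel between them.

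These points limit the consequence. They do not remove the zero score at four of five visits, or the lack of a rule for when the two primary variables disagree.

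**Conclusion.** The point holds for one of the two primary variables. Change from the previous visit measures the RTX response at week 12 and is blind to a held response at weeks 18, 32, 46 and 68; this follows from the schedule alone. If NR-C is still improving and is measured, the variable leans towards NR-C while CAS level leans towards RTX. In the assumed setting with 20 per group, that is 11–24% of trials significantly favouring NR-C against 21–94% significantly favouring RTX. These percentages are illustrations that depend on assumed paths, SDs and group sizes. Following the plan as written could yield a misleading primary result that a wording change would prevent.

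**What to change.** In SAP 2.3.1, for NR-RTX against NR-C:

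1. Replace change from the previous timepoint with change from a fixed reference. Either promote the change from baseline already in SAP 2.3.2, or use week-4 CAS where it is recorded in both non-responder groups.
2. State whether this variable or CAS level decides, and preferably at which visit.
3. Keep visit-to-visit change as descriptive only.

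For the within-group signed-rank test in NR-RTX, do not use week 4 as the sole reference, for the regression-to-the-mean reason above. Report change from baseline as well.

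The cost is SAP wording. The week-4 evaluation is already planned for every study patient. NR-C patients without the chosen reference CAS in the clinic record drop out of the change analysis, but CAS level still includes those measured at the visit. The number lost should be reported.
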